**Multicenter double-blind placebo-controlled randomized
clinical trial of efficacy and safety of Tenoten for children in
the treatment of specific developmental disorders of
scholastic skills in children**

Phase III

Sponsor	ООО «NPF «MATERIA MEDICA HOLDING»
Protocol number	MMH-TD-005
Version date:	January 22, 2015
ClinicalTrials.gov Id:	NCT03159104

Protocol Summary

This document represents the protocol summary for the study on human subjects. The study will be carried out in accordance with ICH GCP, National Standard of the Russian Federation GOST 52379-2005 "Good Clinical Practice", Helsinki Declaration of World Medical Association, relevant requirements of the regulatory authorities as well as the study procedures.

Title of Study

Multicenter double-blind placebo-controlled randomized clinical trial of efficacy and safety of Tenoten for children in the treatment of specific developmental disorders of scholastic skills in children.

Phase: III

Sponsor: OOO «NPF «MATERIA MEDICA HOLDING», Moscow, Russia

Protocol No. MMH-TN-005

Objective of the study

- To evaluate efficacy and safety of Tenoten for children in the treatment of specific developmental disorders of scholastic skills in children.

Endpoints

Primary endpoint

1. Mean total scholastic skill score (reading, spelling and counting) in the groups after 12-week therapy compared to baseline.

Secondary endpoints

1. Mean score of "Reading skill test" in the groups after 12-week therapy compared to baseline.
2. Mean score of "Spelling skill test" in the groups after 12-week therapy compared to baseline.
3. Mean score of subtest No. 3 "Arithmetic" (of Wechsler Intelligence Scale for Children, WISC) in the groups after 12-week therapy compared to baseline.
4. Percentage of children with an increase in total scholastic skill score¹ (reading, spelling and counting) in the groups after 12-week therapy compared to baseline.
5. Efficacy Index according to Clinical Global Impression scaly by the end of therapy (CGI-EI).

¹ Improvement criterion – increased total scholastic skill score (reading, spelling and counting) by at least 5 points compared to baseline.

Safety assessment

- Occurrence and nature of adverse events (AE) during the treatment; AE severity, causal relationship to the study drug, and outcome.

Study design

A multicenter, double-blind, randomized, placebo-controlled clinical trial to evaluate the efficacy and safety of the study treatment.

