The study will enroll the school children (boys and girls) of grades 1, 2 and 3 of a regular school aged 7-9 years old (grade 1 school children will be enrolled at the beginning of the second half of the year) complaining of difficult learning classified according to ICD-10 as specific developmental disorders of scholastic skills (F81) including:

- specific reading disorder (F81.0);
- specific spelling disorder (F81.1);
- specific disorder of arithmetical skills (F81.2);
- mixed disorder of scholastic skills (F81.3);
- disorder simultaneously meeting criteria of F81.2+F81.0 or F81.2+F81.1, or F81.2+F81.0+F81.1.

The developmental disorders of scholastic skills will be verified by a doctor (either a neurologist or psychiatrist) according to reading, spelling, and counting tests. The children may have any concomitant diseases not considered as exclusion criteria and not requiring therapy during the following 12 weeks using the products specified in section "Forbidden concomitant therapy". Specific additional educational programs should not be performed within 12 weeks after enrollment either.

On signing information sheet (informed consent form) by the parent/adopter the patients will be examined by a neurologist or psychiatrist and tested for reading skills (method by L.A. Fotekova, T.V. Akhutina, 2002;), spelling skills (method by L.A. Fotekova, T.V. Akhutina, 2002) and counting skills (subtest No. 3 "Arithmetic" WISC test), and concomitant therapy will be recorded. If inclusion criteria are met and non-inclusion criteria are absent at Visit 1, the patient will be enrolled in the trial and randomized into one of the two groups: 1 tablet of Tenoten for children three times daily for 3 months (group 1) or the same dosing regimen of Placebo (group 2).

At Visit 1 the parents/adopters will receive the study product for 12-week treatment period and a diary to report any potential adverse events and cases of concomitant therapy.

Six weeks later (Week 6±3 days) a "Phone visit" (Visit 2) will be made in order to interview parents about the patient's condition, the presence / absence of concomitant diseases, adverse

events.

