At Visit 3 (Week 12±3 days) repeated testing of reading, spelling and counting skills will be made, complaints, data on concomitant diseases, concomitant therapy, and adverse events will be collected. The investigator will evaluate the subject's compliance and fill in the Clinical Global Impression Scale to calculate Efficacy Index (CGI-EI).

The patients will be allowed to take symptomatic therapy and medications for their co-morbidities during the study, except for the medicines listed in "Forbidden concomitant therapy".

Inclusion and exclusion criteria

Inclusion criteria

1. Children of either gender aged 7 to 9 years old.
2. School children of grades 1-3 (grade 1 children will be enrolled at the beginning of the second half of the year) in regular schools with state accreditation with principal educational program of elementary general education in compliance with Federal State Educational Standard of the Russian Federation.
3. Beginning of the second half of the year (only for 1st grades).
4. Specific developmental disorder of scholastic skills such as:
 - specific reading disorder (F81.0);
 - specific spelling disorder (F81.1);
 - specific disorder of arithmetical skills (F81.2);
 - mixed disorder of scholastic skills (F81.3; i.e. meeting the criteria for one of the following combinations: F81.2+F81.0, F81.2+F81.1, or F81.2+F81.0+F81.1).
5. Reading score of 15 to 35 on the Reading Skills test (L.A. Fotekova, T.V. Akhutina, 2002).
6. Spelling score of 15 to 30 on the Spelling Skills test (L.A. Fotekova, T.V. Akhutina, 2002).
7. Counting score of 5 to 15 on the subtest No. 3 "Arithmetic" (of Wechsler Intelligence Scale for Children).
8. Availability of a patient information sheet (Informed Consent Form) signed by the parent/adopter to confirm the child's participation in the clinical trial.

Exclusion criteria

1. History of the diseases:
 - Diseases of the nervous system, including:
 - inflammatory diseases of the central nervous system,
 - systemic atrophies,
 - extrapyramidal and movement disorders,
 - degenerative diseases of the nervous system,

- demyelinating diseases of the central nervous system,
- episodic and paroxysmal disorders,
- polyneuropathies,
- diseases of myoneural junction and muscle,
- cerebral palsy.
- Congenital malformations of the nervous system (excl. Spina bifida without hydrocephalus).
- Diseases and congenital malformations of eye causing impairment of vision.

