Storage conditions: Store below 25°C. Keep out of the reach of children.

Treatment duration

Tenoten/Placebo treatment duration is 12 weeks.

Observation period

In total the patients will be monitored for 12 weeks.

Symptomatic (Standard) treatment

[figure not shown]
Medicinal products and procedures required for the subjects including for the treatment of underlying and concomitant diseases except for the product included into section “Forbidden concomitant therapy”.

Prohibited concomitant therapy

Within 4 weeks prior to enrollment and throughout the study the subjects are not allowed to use any of the following medications (ATC group is specified in brackets):

1. Psycholeptic drugs (ATC group - N05) including anxiolytics (tranquilizers), hypnotics and sedatives.
2. Psychoanaleptics (ATC group – N06) including psychostimulants and nootropic drugs including:
 - pyrrolidine derivatives (racemates) – piracetam, etiracetam, aniracetam, etc.;
 - pyridoxine derivatives – pyritinol, biotredin;
 - GABA derivatives and analogues – gamma-aminobutyric acid, nicotinoyl gamma-aminobutyric acid, gamma-amino-beta-phenylbutyric acid hydrochloride, hopantenic acid, calcium gamma-hydroxybutyrate;
 - Ginkgo biloba;
 - neuropeptides and their analogues – methionyl-glutamyl-hidtidyl-phenylalanyl-prolyl-glycyl-proline;
 - amino acids and substances affecting excitatory amino acid system – glycine, pyridoxine+threonine;
 - Polypeptides and organic composites - bovine cerebral cortical polypeptides, cerebrolysin;
 - substances from other pharmacological groups with nootropic effect (general tonic drugs and adaptogens – acetylaminosuccinic acid, melatonin, lecithin, etc.).
3. Antiepileptic drugs (ATC group – N03A).
4. Anticholinergic drugs (ATC group – N04A).
5. Dopaminergic drugs (ATC group – N04B).
6. Antihypoxic and antioxidant drugs (ethylmethylhydroxypyridine succinate, citicoline, etc.).
7. Agents improving metabolism and energy supply to tissues, reducing tissue hypoxia (cytoflavin, corylip, eltacin, inosie, etc.).
8. Homeopathic remedies.
9. Drugs known to have caused allergic reactions.
10. Specific additional educational programs (forbidden during the study).

Study design scheme

Schedule of study procedures

Procedure	Visit 1 (Screening, Day 1)	Visit 2 Phone visit (Week 6 ±3 days)	Visit 3 (Week 12 ±3 days)
Informed consent	+		
Collection of complaints	+	+	+
Medical history	+		
Physical examination	+		+
Concomitant therapy	+	+	+

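### Entry is tied to the school calendar for grade 1 only, so the 12-week window of a grade 2-3 child may overlap a holiday, and the between-group test does not allow for it

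*Combined protocol and SAP*

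**What the plan says.** The calendar rule appears in three places in the combined protocol and SAP, each time for grade 1 only:

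- Study design: "grade 1 school children will be enrolled at the beginning of the second half of the year".
- Inclusion criteria, item 2: "School children of grades 1-3 (grade 1 children will be enrolled at the beginning of the second half of the year".
- Inclusion criteria, item 3: "Beginning of the second half of the year (only for 1st grades".

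No entry date, recruitment period or term-time condition is printed for grades 2 and 3.

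The primary endpoint is "Mean total scholastic skill score (reading, spelling and counting) in the groups after 12-week therapy compared to baseline". The second measurement has a fixed distance from the first: "At Visit 3 (Week 12±3 days) repeated testing of reading, spelling and counting skills will be made".

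Teaching during the window is controlled in one respect. Extra programmes are barred, in Study design ("Specific additional educational programs should not be performed within 12 weeks after enrollment either") and in Prohibited concomitant therapy, item 10 ("Specific additional educational programs (forbidden during the study"). The Schedule of study procedures has no entry for ordinary school attendance or term dates.

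Allocation is described without stratification: "the patient will be enrolled in the trial and randomized into one of the two groups". Under Parametric criteria, item 1 assigns Student's test for independent samples to comparisons of continuous variables between groups. Item 3 lists ANOVA or ANCOVA for changes over time, but names no covariate.

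**The concern.** Reading, spelling and counting are taught at school. A child who has lessons throughout the 12 weeks and a child who spends part of them on holiday may gain different amounts whatever the treatment. Because the plan sets no calendar condition for grades 2 and 3, both kinds of window can enter the same change score, and nothing in the stated comparison separates them.

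Two things are at stake:

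- **Precision.** Variation in taught weeks adds to the spread of the change score. It is known in advance and could be removed.
- **Interpretation.** The pooled difference becomes an average over an unspecified mix of taught and partly untaught windows. A reader of the result could not tell which circumstances it describes.

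**Working it through.** **1. The plan's own figure.** Evaluation of sample size gives a margin of 5, an expected difference of 10, SD 12, two-sided alpha 0.05, power 80% and one O'Brien-Fleming look at half the information. The excess over the margin is 10 - 5 = 5.

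- n per group = 2 × 12² × (1.960 + 0.842)² / 5² = 90.4.
- The two-look O'Brien-Fleming factor, computed numerically, is 1.0078: 90.4 × 1.0078 = 91.1, so 92.
- 92 / (1 - 0.30) = 131.4, so 132.

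Both stated figures reproduce; the sample size arithmetic is not at issue. Power at 92 per group (fixed-design formula) is Φ(5 / (12 × √(2/92)) - 1.96) = Φ(2.826 - 1.96) = 81%.

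**2. Assumptions, none of them in the documents.**

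- One long break of B = 8 to 13 weeks per year.
- Grade 2-3 children enter evenly over the 52 - B term weeks.
- One third of children are in grade 1 and lose no taught weeks.
- The ordinary taught gain is G = 10 to 15 points per 12 weeks and accrues evenly over taught weeks.
- The stated SD of 12 does not already contain calendar variation.

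**3. Weeks lost by a grade 2-3 child.** Only starts in the last 12 weeks before the break overlap it. A start that puts t weeks of the window past the last school day loses min(t, B) weeks.

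| | B = 8 | B = 13 |
|---|---|---|
| Any overlap | 12/44 = 27% | 12/39 = 31% |
| At least 6 of 12 weeks lost | 6/44 = 14% | 6/39 = 15% |
| Mean weeks lost | 64/44 = 1.45 | 72/39 = 1.85 |
| Mean square | 426.7/44 = 9.70 | 576/39 = 14.77 |

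**4. All children, one third with no loss.** Variance of weeks lost = (2/3) × mean square - ((2/3) × mean)².

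- B = 8: 6.46 - 0.94 = 5.52 (SD 2.35 weeks).
- B = 13: 9.85 - 1.51 = 8.33 (SD 2.89 weeks).

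**5. Effect on SD and power.** SD = √(144 + (G/12)² × variance from step 4). Power = Φ(5 / (SD × √(2/92)) - 1.96).

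| B | G | Added variance | SD | Power at 92 |
|---|---|---|---|---|
| 8 | 10 | 3.84 | 12.16 | 79.6% |
| 8 | 15 | 8.63 | 12.35 | 78.4% |
| 13 | 10 | 5.79 | 12.24 | 79.1% |
| 13 | 15 | 13.02 | 12.53 | 77.2% |

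Restoring 80% would take 94 to 100 completers per group (step 1 with these SDs) instead of 92.

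**6. Sensitivity.** With no grade 1 children, the SD is 12.2-12.7 and power 76-79%. If Visit 1 could also fall inside the break, it is 12.2-13.0 and 74-79%.

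**7. If the treatment effect itself were smaller in holidays.** Only the part of the effect above 5 points counts towards rejection. If the average effect fell from 10 to 9, power at SD 12 would be Φ(4/1.769 - 1.96) = 62%. This shows how sensitive the test is. The documents give no basis for saying that any such loss occurs.

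**The case against.** **The overlap is permitted, not planned.** The document describes itself as a protocol summary and prints no recruitment dates for any grade. Recruitment might in practice fall wholly in term. This stands, and the point is limited to what the text allows. A reader might also infer that grade 2-3 windows would lie mostly in the summer break. Under the assumptions above, only 14-15% of them lose half or more of their weeks.

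**The grade 1 rule may have another purpose.** A reader might take it as the plan's own admission that schooling during the window drives the outcome. It may equally be there because first-graders need some months of teaching before these skills can be tested and a disorder verified. No reason is stated, so the rule supports neither inference.

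**Bias.** A reader might infer that the comparison is biased. It is not: holiday windows fall on both arms by chance. Taught time can differ between grades, but not systematically between arms.

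**The loss may be smaller still.** The SD is stated as at least 12 points for the trial outcome, so it may already include calendar variation, and adding that variation would count it twice. The interim analysis for sample size adjustment could also respond to excess variance. Both points stand against the precision cost; neither makes clear what the pooled effect describes.

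**ANCOVA and mixed models are already listed.** They are, but generically. Neither grade nor school time is named, and the entry for two independent groups is the t-test.

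**Averaging over the school year is a legitimate pragmatic choice.** This stands, and it is why restricting entry is not put forward as a required change.

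**Conclusion.** The gap is in the text: the calendar rule covers grade 1 only, nothing keeps a grade 2-3 window in term, and the stated between-group test does not account for it. The consequence is extra variance and a less clear estimand.

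The variance cost is modest: about 1 to 4 points of power (77-80% against 81%), conditional on the assumed break length, term-time entry, grade mix and taught gain. A much larger loss follows only if the effect is taken to be proportional to taught weeks. No section states such a mechanism, so that reading is not supported. Some loss of effect in holidays remains possible and would be costly against a 5-point margin, but its size cannot be derived from the documents.

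This is a worthwhile improvement to the analysis and does not undermine the design.

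**What to change.** **Change.** Make the primary comparison an ANCOVA of the 12-week change in total score, with treatment, grade (1/2/3) and number of scheduled school weeks in the child's window as prespecified terms. Test the adjusted treatment difference against the same 5-point margin.

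Derive scheduled school weeks from the Visit 1 date and the school calendar over the nominal 12 weeks, not from the actual Visit 3 date or attendance. It is then fixed at randomisation and is a proper baseline variable. As a supportive analysis, report the treatment difference in children whose whole window is in term.

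**Cost.** Term dates must be looked up for each site or school, because the Schedule of study procedures does not collect them. There is a little more analysis work. No patients, visits or tests are added. Adjustment recovers precision, but it cannot restore an average effect that holidays have reduced; the supportive analysis would help to show whether that happened.

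**Option, not required.** The sponsor may restrict grade 2-3 entry to dates that keep the whole window in term. That would sharpen the question, but it closes part of the enrolment year, slows recruitment and narrows what the trial estimates. If it is adopted, the school-weeks covariate would have little variation left.

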13. Patients whose parent(s)/adopter(s) work for OOO "NPF "MATERIA MEDICA HOLDING" (i.e., is the company's employee, temporary contract worker, or, designated officials responsible for carrying out the research or any immediate relatives of the aforementioned).

Criteria for Withdrawal or Termination

1. Failure or refusal of parents/adopters to follow the protocol requirements.
2. Necessity for prescribing medications not permitted during the study.
3. An adverse event requiring discontinuation of the study drug.
4. Parent /adopter's decision to withdraw early for lack of efficacy or other reasons.
5. Cases not stipulated in the protocol where the investigator decides that further participation may harm the patient.
6. Eligibility error.

Number of subjects

It is planned to include 264 subjects, which is expected to yield at least 184 patients (92 x 2 groups) patients completing all protocol procedures.

Interim analysis

An interim analysis is planned for potential adjustment of sample size.

² 1 unit of alcohol is equivalent to 0.33 L of lager/150 mL of unfortified wine, or 40 mL of Ethyl Alcohol.

Treatment

Group 1

Name of the medicinal product: Tenoten for children

Active ingredient: Affinity purified antibodies to brain-specific S-100 protein - 0.003 g*

* added to lactose monohydrate powder as a water-ethanol mixture containing not more than 10-16 ng/g of an activated form of the active substance.

Excipients: Lactose monohydrate - 0.267g

 Microcrystalline cellulose - 0.03 g

 Magnesium stearate - 0.003 g

Method of administration: Tablet for oral use. Dose per administration: 1 tablet. 1 tablet three times daily (3 tablets per day). The tablets should be held in the mouth until complete dissolution, without meal.

Dosage form: Tablets.

Description: White to off-white, round, flat, scored on one side and beveled tablets.

Storage conditions: Store below 25°C. Keep out of the reach of children.

Group 2

Name of the medicinal product: Placebo

Active ingredient: NA

Excipients: Lactose monohydrate - 0.267 g

 Microcrystalline cellulose - 0.03 g

 Magnesium stearate - 0.003 g

Method of administration: Tablet for oral use. Dose per administration: 1 tablet. 1 tablet three times daily (3 tablets/day). The tablets should be held in the mouth until complete dissolution, without meal.

Dosage form: Tablets.

Description: White to off-white, round, flat, scored on one side and beveled tablets.

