Examination of reading skills (method by L.A. Fotekova, T.V. Akhutina, 2002)	+		+
Examination of spelling skills (method by L.A. Fotekova, T.V. Akhutina, 2002)	+		+
Examination of counting skills ("Arithmetic" subtest No. 3 of WISC)	+		+
Inclusion/exclusion criteria	+		
Randomization and prescription of study therapy	+		
Study drug supply	+		
Study drug accountability, compliance assessment			+
Distribution of diaries	+		
Evaluation of correct diary filling			+
Diary return			+
CGI-EI scale filling			+
Evaluation of treatment safety	+	+	+

Statistical Analyses

Samples

Total set includes all the subjects who have signed ICF. This sample will consider all adverse events throughout the study, including those occurred prior to the study therapy.

The sample including all subjects who received at least one dose of the study product to be used for ***analysis of the study treatment safety and tolerability*** (*Safety population*), as all adverse events identified after the study product administration will be recorded.

Full Analysis Set This sample will consist of all enrolled subjects, except for those who met at least one of the following criteria:

- 1) failure to meet inclusion/non-inclusion criteria;
- 2) subject failing to take any dose of the study drug;
- 3) absence of any data on the subject after randomization.

This was the best set for the Intention-to-treat method, so it will be used in the ***Intention-to-treat efficacy analysis of the test therapy***.

Per Protocol set. This sample includes all subjects who completed the therapy as per the study protocol, without any missing visits or major protocol deviations. This set will be used in the ***Per Protocol efficacy analysis of the test therapy***.

Mean value of the total set for the relevant day will be used to fill lacking/missing data.

Data treatment and all statistical calculations under the protocol will be made using SAS-9.3 statistical software.³

Evaluation of sample size

The sample size was assessed in accordance with the following rules and assumptions:

1. Statistical assumptions:

- 1.1 the power of statistical tests is 80% (the probability of correct rejection of the null hypothesis is 0.8)
- 1.2 the probability of type 1 error ' α ' is less than 0.05 (the probability of false acceptance of the alternative hypothesis)
- 1.3 statistical criteria used are two-sided

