- 1.4 value of clinically relevant " δ " difference is taken as equal to 5 (i.e. Tenoten for children effect is supposed to be clinically relevant compared to placebo effect if the effect in the study group exceeds the one in control group by at least 5 points)
- 1.5 statistical null and alternative hypotheses will be as follows:

³ Holder of license: OOO "NPF "MATERIA MEDICA HOLDING", No. 70100045.

$$H_0: m_1 - m_2 \leq \delta$$

$$H_1: m_1 - m_2 > \delta,$$

where m_1 - mean total scholastic skill score in Tenoten for children group

m_2 – mean total scholastic skill score in placebo group

δ – clinically relevant difference value.

1.6 an interim analysis is planned for potential adjustment of sample size:

- a. calculations will be made using O'Brien-Fleming boundary;
- b. proportions of the subjects completing the study and yielding the results for interim and final analyses, will be taken as 0.5 and 1.0 (i.e. interim analysis will be made after recruitment of half of the planned number of the clinical study subjects).

1.7 therefore, sample size will be calculated taking into account:

- a. interim analysis;
- b. assumption on expected effects declared in the main efficacy criterion of the protocol.

1.8 calculation of sample size in groups 1 and 2 for two-sided test for interim and final analysis will be made using the formula defining sample size (i.e. for the variant without interim analysis):

$$N_1 = N_2 = (\sigma_1^2 + \sigma_2^2) I,$$

where N_1 and N_2 are sample sizes in Tenoten for children and placebo groups

σ_1 and σ_2 – expected standard deviations in these groups

I – Fisher information determined using the formula:

$$I = (F^{-1}(1-\alpha) + F^{-1}(1-\beta))^2 / \theta_1^2,$$

where $F^{-1}(1-\alpha)$ and $F^{-1}(1-\beta)$ are tabular z-test values for α and β , a $\theta_1 = (m_1 - m_2)$.

1.9 final sample size will be determined using the formula:

$$N_F = N_{PP} / (1 - C_w),$$

where N_F – final sample size;

N_{PP} – result of calculation in cl. 1.8, i.e. scheduled number of subjects

completing the study per protocol;

C_w – withdrawal coefficient.

2. Assumptions on expected clinical study effects:

The difference between Tenoten for children effect consisting in increased mean total scholastic skill score by the end of therapy and effect in placebo group is supposed to be at least 10 points with standard deviation of at least 12 points.

Given the statistical terms and assumptions above each group size will be:

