- a) at interim analysis - 46 subjects
- b) at final analysis - 92 subjects.

Therefore, total PP set will include 184 subjects.

Taking into account that potential withdrawal of 30% subjects at the screening and during the study for various reasons, at least **132** subjects in each group will be required to sign informed consent (in total **264** subjects).

Statistical criteria

All statistical calculations will be made using two groups of statistical criteria:

- parametric - to evaluate continuous and interval random values;
- nonparametric – to obtain:
 - evaluations of equality/inequality of proportions of the subjects upon their comparison for various visits,
 - analysis of frequencies of the features compared,and
 - evaluation of continuous and interval random values in case of non-compliance with normal random distribution.

The following SAS procedures are suggested for interim analysis:

- SEQDESIGN, SEQTEST – design and performance of interim analysis;
- The terms of early termination of the study will be set using O'Brien-Fleming stopping boundary.

Parametric criteria

Prior to analysis using parametric statistics, data samples under comparison will be tested for normality (the Kolmogorov-Smirnov test).

The following parameters and approaches are to be used:

1. To evaluate the differences in continuous variables from two different (independent) groups – Student's test for independent samples.
2. To evaluate differences in continuous variables in one group at two different visits - Student's test for paired samples.
3. To evaluate time changes in parameters compared - analysis of variance (ANOVA) or modified repeated measures covariance (ANCOVA).
4. In case of multiple comparisons of the groups various corrections for multiplicity will be used, e.g. Dunnett, Tukey, Scheffe, Holm adapted test, etc.
5. Generalized Linear Models will be used in case of abnormal data distribution.

6. Selection of the type of distribution, specification of factor and covariance structures of the model will be made using fit-statistics such as AIC (Akaike information criterion).

The following SAS software programs are supposed to be applied to the above listed tests and techniques:

- UNIVARIATE: normality verification of the distributions under comparison;
- CORR, MEANS - calculation of descriptive statistics
- TTEST – Student's test with all modifications
- GLM – generalized linear models for analysis of time changes (ANOVA, ANCOVA)

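### No Week-12 testing is stated for children who stop the study product, so those lost before Visit 3 have no primary outcome and, if kept in the Full Analysis Set, receive a filled-in mean

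*Combined protocol and SAP*

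**What the plan says.** The section Criteria for Withdrawal or Termination has six items. Some concern the study product: an adverse event that requires stopping it, or "Necessity for prescribing medications not permitted during the study". Others concern leaving the study: "Parent /adopter's decision to withdraw early for lack of efficacy or other reasons". The list does not separate the two kinds and does not say what is measured afterwards.

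In the Schedule of study procedures, the three skill tests appear at Visit 1 and at Visit 3 (Week 12) only. Visit 2 is a telephone contact. There is no early-termination visit.

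Under Statistical Analyses, Samples, the rule for gaps is: "Mean value of the total set for the relevant day will be used to fill lacking/missing data". The same section defines the total set as everyone who signed consent. The FAS, named for the intention-to-treat analysis, drops children who fail eligibility, took no dose, or have no data after randomisation. The Per Protocol set drops children with a missed visit.

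Evaluation of sample size sets the allowance for losses: "Taking into account that potential withdrawal of 30% subjects at the screening and during the study". It is applied to consent signers, 132 per group (264 in total), to leave 92 per group (184).

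**The concern.** The primary endpoint has one post-baseline measurement. A child who stops the product at Week 4 and is then treated as withdrawn contributes nothing to it, even if the family would have come back at Week 12. If the Week-6 call was made, that child has data after randomisation, stays in the FAS, and is given an average score.

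Lack of efficacy, adverse events and a need for prohibited medication are all plausibly linked to how the child is doing. An overall mean removes that information. If it is pooled over arms, it also gives filled children in both groups the same value, so they add no difference between the groups. The direction of the resulting bias depends on who leaves which arm and why, and the documents do not allow it to be predicted. With no intermediate skill test, a better imputation model would have little on-treatment information to use. Observed Week-12 scores would address the problem more directly.

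**Working it through.** **Inputs.** From Evaluation of sample size: "the power of statistical tests is 80"%; alpha 0.05; "statistical criteria used are two-sided"; the clinically relevant "difference is taken as equal to 5"; expected difference 10, SD 12; one O'Brien-Fleming interim at half the information; 30% loss.

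**1. The plan's own figure.** Testing against the 5-point margin leaves 10 − 5 = 5 to detect. n = 2 × 12² × (1.960 + 0.842)² / 5² = 90.42. The O'Brien-Fleming inflation, solved numerically, is 1.0078: 90.42 × 1.0078 = 91.12, rounded up to 92. Then 92 / 0.70 = 131.4, rounded up to 132 per group. Both figures reproduce.

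**2. How many outcomes are at risk.** The allowance is 264 − 184 = 80 consent signers (30.3%). If a share s fails screening, 264(1 − s) are randomised and 264(1 − s) − 184 are lost afterwards. The documents do not give s, so these values are assumed.

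| s | Randomised | Lost after randomisation | Share of randomised |
|---|---|---|---|
| 0% | 264 | 80 | 30% |
| 10% | 238 | 54 | 23% |
| 20% | 211 | 27 | 13% |
| 25% | 198 | 14 | 7% |

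The number filled in is lower still, because some of these children fall out of the FAS.

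**3. Effect of the fill.** Assume a mean pooled over arms and the same fraction f filled in each arm, with N = 132. The expected difference is 10(1 − f). The within-arm variance is (1 − f)·144 + f(1 − f)·25, because the filled value lies 5 points from each arm mean. The calculated standard error is √(2·variance/N). The actual one is √(2·144·(1 − f)/N). The chance of success is Φ[(difference − 5 − 1.96 × calculated SE) / actual SE].

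| f | Difference | Calculated SE | Actual SE | Chance of exceeding 5 |
|---|---|---|---|---|
| 0 | 10.0 | 1.477 | 1.477 | 92% |
| 10% | 9.0 | 1.413 | 1.401 | 81% |
| 20% | 8.0 | 1.344 | 1.321 | 61% |
| 30% | 7.0 | 1.268 | 1.236 | 35% |

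Holding N at 132 flatters the 10% and 20% rows, since 132 are randomised only if nobody fails screening. With 92 completers and 10% filled, N = 92/0.9 ≈ 102, the calculated SE is √(2 × 131.85/102) = 1.608, the actual SE is √(0.9 × 288/102) = 1.594, and the chance is Φ[(4 − 3.152)/1.594] ≈ 70%.

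**4. Where the loss comes from.** Analysing 92 observed children per group with no fill gives SE = 12√(2/92) = 1.769 and power Φ(5/1.769 − 1.96) = 81%. At 30% loss, the missing data alone cost 92% to 81%. The fill rule accounts for the rest, 81% to 35%.

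**5. What Week-12 testing would change.** Suppose 30% leave, half of them are tested and half filled, N = 132, and tested leavers in the Tenoten group keep a share r of the effect. The half and the r values are assumptions. The expected difference is 10(0.70 + 0.15r). The variances follow as in step 3, with the added spread between completers and leavers in the Tenoten group.

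| r | Difference | Calculated SE | Actual SE | Chance of exceeding 5 |
|---|---|---|---|---|
| 1 | 8.5 | 1.379 | 1.362 | 72% |
| 0.5 | 7.75 | 1.385 | 1.370 | 51% |
| 0 | 7.0 | 1.407 | 1.396 | 29% |

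The comparison without testing is 35%, so the result can move either way.

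**The case against.** The strongest reply is that the trial is sized for 184 completers and the 30% allowance already pays for losses. This holds for precision: 92 observed per group give the intended power. It does not answer the bias, because the FAS is not an analysis of those 184 completers. It also contains children with filled scores.

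A reader might infer that up to 30% of outcomes will be lost and replaced. The documents do not support that. The allowance includes screening losses, and three test-score ranges plus a long exclusion list make zero screening failures unlikely. The FAS also drops some losses instead of filling them. Nor does the intention-to-treat analysis rest chiefly on invented values, since most FAS scores would be observed.

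A reader might also infer that the plan rules out testing after withdrawal. It does not. The public text calls itself a summary and says children are monitored for 12 weeks in total, without saying whether this continues after withdrawal. The supportable statement is that no follow-up rule is given.

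Two further objections stand. Scores obtained after prohibited therapy answer a treatment-policy question, so less bias means less bias for that estimand. And some families who refuse or withdraw will not return whatever the protocol says.

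**Conclusion.** The point stands in this form: no Week-12 test is stated for children who stop the product or meet a withdrawal criterion, Visit 3 is the only post-baseline test, and children who remain in the FAS without it receive a mean. Following the text as written weakens the intention-to-treat analysis, so this is more than missing detail.

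The size is uncertain. Between about 7% and 30% of randomised children could be affected, depending on an assumed screening loss of 25% to 0%, less the FAS exclusions. The 81/61/35% figures for 10/20/30% filled depend on a fill pooled over arms, equal fractions in each arm, the plan's difference of 10 and SD of 12, and 132 randomised per group. They should not be charged to the missing visit alone, because the fill rule causes most of the drop. It would also be wrong to promise more power from the repair: the range in the half-tested scenario is 72% down to 29%, and the favourable end assumes that leavers keep the whole effect. The case for acting is that observed outcomes replace constants at little cost.

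**What to change.** Leave the rules for stopping treatment as written. Add a statement that eligible randomised children who stop the study product are still invited to the scheduled Visit 3 reading, spelling and counting tests, unless the parent withdraws consent or the investigator judges that continuing could harm the child. State that these scores enter the FAS in place of filled values and that any prohibited therapy is recorded. Concomitant therapy is already collected at each visit. The FAS exclusions, including the one for eligibility errors, and the Per Protocol set stay as they are, and so does the sample size.

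The cost is one or two protocol sentences and site effort to bring children back. No visit or test beyond the scheduled Visit 3 is added. The FAS estimate becomes a treatment-policy effect, which may be smaller than the effect in children who complete treatment, and the protocol should say so. The fill rule would still apply to children who do not return and needs its own repair.
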